#### Risk Benefit assessment

In the current study, E7766 is being evaluated for the treatment of solid tumors or lymphomas, that are advanced, nonresectable, or recurrent and progressing since last antitumor therapy, and for which no alternative standard therapy exists. E7766 is a new agent with a novel mechanism of action and has demonstrated a potent and long lasting antitumor activity in nonclinical tumor models with nonsevere toxicity through intratumoral administration. Based on the antitumor activity of E7766 observed in nonclinical tumor models, E7766 is expected to demonstrate clinical activity and response in these subjects, for whom no alternative standard therapy exists and the prognosis is poor.

Eisai Confidential Page 47 of 138

Nonclinical safety assessments were conducted in mice and cynomolgus monkeys and they showed adverse effects consistent with the pharmacologic activity. Based on these studies, the following adverse effects may be anticipated in the FIH study:

- Systemic inflammation, manifested as described in the next 2 bullets below
- Cytokine elevation, including of IL-6, IP-10, MCP-1, IFNβ, and TNF-α, peaking at approximately 8 hours postdose, and which is likely to be markedly lower after 24 hours. The amplitude of cytokine response is not expected to change significantly upon repeated dosing.
- Local injection site irritation including reddening, swelling, and ulceration.
- Gastrointestinal signs, including diarrhea

Overall, considering the promising antitumor activity and limited toxicity of E7766 in nonclinical studies at the doses showing antitumor activity when administered via the intratumoral route, clinical evaluation of E7766 via the intratumoral route is planned in subjects with advanced solid tumors and lymphomas.

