- c. In the Dose Escalation part, subjects will be admitted at Baseline and on Cycle 1 Day 14 to the study clinic. In the Dose Escalation part, on Day 1 of Cycle 1 (ie, after the first dose only), subjects will remain at the study clinic for at least 30 hours after E7766 administration for monitoring of safety and can be discharged on Cycle 1 Day 2 if there are no safety concerns.
- d. A comprehensive physical examination will be performed at Screening and at the Off-Treatment Visit. A symptom-directed physical examination will be performed on Day 1 of all treatment cycles and at any time during the study, as clinically indicated. Vital signs include BP, HR, RR, and body temperature, as well as weight and height. BP, HR, and RR will be collected after the subject has been sitting for 5 minutes. Height will be measured at the Screening Visit only. On all dosing days, vital signs should be measured prior to dosing. On Day 1 of Cycle 1, vital signs should be obtained postdose within 2 hours of dosing, and subsequently every 4 hours or as clinically indicated for 30 hours postdose. On the other dosing days, vital signs should be assessed postdose within 2 hours of dosing. Vital signs will also be assessed at the Off-Treatment Visit.
- e. Echocardiograms or MUGA will be performed at Screening, during the Off-Treatment Visit (window of ±1 week), and if clinically indicated. MUGA scans and echocardiograms will be performed locally in accordance with the institution's standard practice.
- f. A serum pregnancy test (β-hCG) will be performed at Screening for all premenopausal women and postmenopausal women who have been amenorrheic for less than 12 months. A urine or serum pregnancy test will be performed at Baseline, before the first dose of E7766 on Cycle 1 Day 1, on Day 1 of all subsequent cycles before E7766 dosing, and at the Off-Treatment Visit.
- g. 12-Lead ECGs will be collected locally at the following time points: Screening (single) and Baseline (single unless abnormalities are observed or if clinically indicated, then in triplicate at 2-minute intervals); Day 1 of all Cycles (before and after [within 1 to 2 hours after E7766 injection]); and at Off-Treatment Visit. In case of any alteration, or if clinically necessary, an echocardiogram and/or cardiac enzymes should be performed.

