- h. Continuous time matched Holter-ECGs to be collected on the day prior to first and third administration of E7766 in Cycle 1, ie, Day -1 and Day 14; and on Cycle 1 Day 1 and Day 15. Replicate 12-lead ECGs will be extracted from the recordings at predose, at end of E7766 administration, and at 0.25, 0.5, 1, 1.5,

Eisai Confidential Page 90 of 138

	Phase	PRETREA	TMENT			TRE	ATMEN	T b		E	XTENSI	ON	Off- Treatment b	FOLLOW- UP PHASE
	Period	Screening	Baseline	Cycle 1 (Induction Cycle)						Cyc	ele 2	Cycle 3 and beyond	Within 30 days	
	Visit	1	2	3	3 3 4 5 5 5					6	7	8, 9, etc	98	100
	Day	-28 to -1	-3 to -1	1	1 2 8 14 15 16					1	15	1		
CRF	Procedures/Assessments													

- 2, 3, 4, 5, 6, 8, 10, 12, and 24 hours after the start of E7766 administration on both days. Subjects must be recumbent for a period of approximately 10 minutes before each time point. If possible, subjects will be encouraged to eat the same or similar food at the same time on all days that the Holter ECGs are conducted. Holter monitoring will be done only during the Dose Escalation part of the study.
- Hematology and blood chemistry samples will be obtained before drug administration. Screening assessments may be used as baseline assessments if
  performed within 72 hours of the first dose of study medication. On Cycle 1 Day 1 before drug administration and at 6 hours and 24 hours posttreatment; on
  Cycle 1 Days 8 and 15 before drug administration, and from Cycle 2 onwards, Day 1 only predose, and at the Off-treatment Visit.
- j. Urine samples will be obtained Screening, Baseline, and before all drug administration (either formal urinalysis or urine dipstick for protein and glucose are acceptable) and at the Off-Treatment visit.

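### In Dose Escalation, no temperature, blood pressure or respiratory rate is scheduled around the expected 8-hour cytokine peak after the Cycle 1 Day 15 injection

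*Protocol*

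**What the plan says.** Footnote d of Protocol Table 7 (Section 9.5.2.1) requires vital signs before every dose. After the first dose it asks for a set within 2 hours and then "subsequently every 4 hours or as clinically indicated for 30 hours postdose". For all later injections the rule is: "On the other dosing days, vital signs should be assessed postdose within 2 hours of dosing". Table 7 marks the next set after Day 15 on Day 16, without a clock time. Protocol Section 9.5.1.5.4 refers back to Table 7 and adds only repeat readings when blood pressure is raised.

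The risk-benefit text in Protocol Section 7.2 anticipates cytokine elevation "peaking at approximately 8 hours postdose", and adds: "The amplitude of cytokine response is not expected to change significantly upon repeated dosing".

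In Dose Escalation, footnote c says that "subjects will be admitted at Baseline and on Cycle 1 Day 14 to the study clinic", and Table 7 marks discharge on Day 16. Footnotes h, k and p set serial Holter, PK and cytokine time points on Day 15. The Holter extractions continue at "2, 3, 4, 5, 6, 8, 10, 12, and 24 hours after the start of E7766 administration on both days".

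**The concern.** Taken at its word, the protocol expects Day 15 to carry a cytokine response much like that of Day 1. Yet the scheduled vital signs stop within 2 hours and resume the next day, so the expected peak falls where nothing is scheduled. Day 15 lies in Cycle 1, the DLT period. Table 5 grades cytokine release storm partly by fever (Grade 1) and hypotension (Grade 2 and above), both of which vital signs record.

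The other scheduled Day 15 measurements do not fill the interval. Haematology and chemistry are predose only. Local 12-lead ECGs are not scheduled that day. Holter gives heart rate, but not temperature, blood pressure or respiratory rate. Site IL-6 testing is only as clinically indicated, and nothing says that the serial cytokine results come back in real time.

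What is at stake is modest: uniform recording of a transient fever or fall in blood pressure near the expected peak, and a temperature and blood pressure readout to set beside the Day 15 cytokine curve. Checks left to discretion may differ between sites and may not reach the CRF.

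**Working it through.** The plan gives no figure of its own to reproduce. The check is a count of the Cycle 1 Day 15 schedule in Dose Escalation.

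**Time points after 2 hours and before 24 hours**

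| Assessment | Source in Table 7 | Hours postdose | Count |
|---|---|---|---|
| Holter extraction | footnote h | 3, 4, 5, 6, 8, 10, 12 | 7 |
| PK blood | footnote k | 3, 4, 6, 8, 10, 12 | 6 |
| Cytokine blood | footnote p | 4, 6, 8, 10 | 4 |
| Vital signs | footnote d | none before the Day 16 set | 0 |

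The union of the first three rows is 7 distinct time points. The zero runs up to the Day 16 set; it extends to 24 hours only if that set is not taken earlier.

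**Comparison with Day 1.** If the first set is at 2 hours and the 4-hourly option is followed, sets fall at 6, 10, 14, 18 and 22 hours: 5 before 24 hours.

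**Distance to the expected peak.** The last scheduled set is at 2 hours at the latest, so it precedes the peak by at least 8 − 2 = 6 hours.

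**Length of the interval.** This is the time of the Day 16 set minus at most 2 hours.
- If the Day 16 set is taken with the 24-hour draw: at least 24 − 2 = 22 hours.
- If it can be taken any time after midnight, and dosing is assumed to be between 08:00 and 12:00: Day 16 begins 16 to 12 hours postdose, so the interval is at least 12 − 2 = 10 hours (12:00 dosing) to 16 − 2 = 14 hours (08:00 dosing).

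The 8-hour peak lies inside the interval in each of these cases.

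**After adding sets at 4, 8 and 12 hours.** The longest interval from dosing to 12 hours is 4 hours. The 4 and 8-hour points already have Holter, PK and cytokine samples; the 12-hour point has Holter and PK.

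**Fit with the Holter.** Footnote h says: "Subjects must be recumbent for a period of approximately 10 minutes before each time point". Footnote d says: "BP, HR, and RR will be collected after the subject has been sitting for 5 minutes". The two postures cannot coincide, so the seated set must follow the recumbent window. The tightest case is 4 hours, because the next extraction is at 5 hours. A set of up to 10 minutes ends at about 4 h 10 min, and the next recumbent window opens at about 5 h − 10 min = 4 h 50 min.

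**Burden.** 3 × 35 = 105 sets and 3 × 40 = 120 sets. At an assumed 5 to 10 minutes each, including the seated wait: 3 × 5 = 15 to 3 × 10 = 30 minutes per subject, and 105 × 5 / 60 = 8.75 to 120 × 10 / 60 = 20 hours in total.

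**The case against.** The strongest reply is that tapering is a reasonable choice. Every subject is watched closely to 30 hours after the first injection. If the amplitude of response does not change much, that subject's response has already been characterised. On Day 15 the subject is in the clinic with continuous Holter, examination at any time as clinically indicated, AE collection on Days 15 and 16, and dose rules for cytokine release storm in Table 4. All of this stands and limits the importance of the point. It does not put a scheduled temperature, blood pressure or respiratory rate near the Day 15 peak.

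A reader might infer that subjects go unobserved for 22 hours, or that a DLT would be missed and the next dose set too high. The documents support neither. Nothing bars extra checks in the clinic, and severe cytokine release storm would be recognised clinically. A missed Grade 1 fever would leave the Table 2 step unchanged, because that row already covers toxicity up to Grade 1. Only a related event of Grade 2 or higher would alter it, and there is no basis for putting a probability on missing one in an inpatient.

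Hypoxia is also part of Table 5, but oxygen saturation is not in the footnote d set, so extra sets would not capture it and it forms no part of the rationale.

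Two further objections have some force. Badly ordered activity could separate the PK draw from its paired ECG and harm the concentration-QTc analysis; the fix therefore has to state the order. The Holters are time matched to Day 14, where no seated sets would be added. However, each set would follow its extraction, and footnote h controls posture only for the minutes before each time point.

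Cycle 1 Day 8 has the same 2-hour rule but no scheduled admission. It is a different trade-off and is not covered here.

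**Conclusion.** The point holds as a cheap improvement to the schedule. In Dose Escalation, the Day 15 injection has no scheduled temperature, blood pressure or respiratory rate from at most 2 hours postdose until an untimed Day 16 set, while seven other time points are served between 3 and 12 hours. The schedule reading is firm; the clinical gain is modest.

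It rests on three things: the 8-hour figure, which is an expectation from nonclinical studies; that timing carrying over to the third injection, where the protocol speaks only of amplitude; and the Day 16 set being taken after the peak. The 22-hour length is conditional on the last set being taken with the 24-hour draw. It is not a finding that safety oversight was absent or that any DLT classification or dose decision is wrong.

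SAP Section 7 records early termination of escalation, and SAP Section 3.2.2 records that no subjects will enter expansion. The value now is for any further use of this schedule.

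**What to change.** Amend footnote d for Dose Escalation so that on Cycle 1 Day 15 temperature, blood pressure, pulse and respiratory rate are also recorded at the existing 4, 8 and 12-hour time points. State the order at each: recumbent Holter window, blood draw at its nominal time, then 5 minutes seated and the vital signs. Time the Day 16 set at about 24 hours.

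Label each set with its nominal time on the CRF. SAP Section 8.1 keeps one record per subject per visit for by-visit summaries, so unlabelled sets would compete for that slot. The listing planned in SAP Section 5.6.4 would show all sets; if they are to be tabulated, add a by-time-point line to the SAP.

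The cost is three sets per subject, or 105 to 120 in total and about 9 to 20 nursing hours on the assumption above, plus three rows on the Day 15 vital-sign CRF page. It needs no new visit and no longer stay.

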## 9.5.2.2 Description of Procedures/Assessments Schedule

Refer to Schedule of Procedures/Assessments in Table 7 and footnotes therein for description of procedures.

# 9.5.3 Appropriateness of Measurements

All clinical assessments are standard measurements commonly used in studies of oncology studies.

The safety assessments to be performed in this study, including hematology analyses, blood chemistry tests, urinalysis, and assessment of AEs, are standard evaluations to ensure subject safety.

- 9.5.4 Reporting of Serious Adverse Events, Pregnancy, and Events Associated with Special Situations
- 9.5.4.1 Reporting of Serious Adverse Events

All SERIOUS ADVERSE EVENTS, regardless of their relationship to study treatment, must be reported on a completed SAE form by email or fax as soon as possible but no later than 1 business day from the date the investigator becomes aware of the event.

All SERIOUS ADVERSE EVENTS, regardless of their relationship to study treatment, must be reported on a completed SAE form by email or fax as soon as possible but no later than 24 hours from when the investigator becomes aware of the event.

Serious adverse events, regardless of causality assessment, must be collected through the last visit and for 90 days after the subject's last dose or start day of another anticancer therapy, whichever is earlier. If the subject initiates new anticancer therapy within 30 days, then SAEs will be collected for 30 days following the last dose of E7766. All SAEs must be followed to resolution or, if resolution is unlikely, to stabilization. Any SAE judged by the investigator to be related to the study treatment or any protocol-required procedure should be reported to the sponsor regardless of the length of time that has passed since study completion.

The detailed contact information for reporting of SAEs is provided in the Investigator Study File.

**For urgent safety issues**, please ensure all appropriate medical care is administered to the subject and contact the appropriate study team member listed in the Investigator Study File.

It is very important that the SAE report form be filled out as completely as possible at the time of the initial report. This includes the investigator's assessment of causality.

Eisai Confidential Page 95 of 138

Any follow-up information received on SAEs should be forwarded within 1 business day of its receipt. If the follow-up information changes the investigator's assessment of causality, this should also be noted on the follow-up SAE form.

Preliminary SAE reports should be followed as soon as possible by detailed descriptions including copies of hospital case reports, autopsy reports, and other documents requested by the sponsor.

The investigator must notify his/her IRB/IEC of the occurrence of the SAE in writing, if required by their institution. A copy of this communication must be forwarded to the sponsors or third party vendor acting on behalf of the sponsors to be filed in the sponsor's Trial Master File.

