#### Extension Phase

In the Extension Phase, subjects who are receiving study drug at the end of the Treatment Phase will continue to receive drug treatment at the same dose, and according to the Dosing Schedule described under "Study Treatment."

In the *Treatment* and *Extension Phases*, subjects will discontinue study drug at the time of confirmed disease progression (per iRECIST or LYRIC), disappearance or nonavailability of any injectable lesions, development of unacceptable toxicity, subject request, withdrawal of consent, termination of the study program, pregnancy, or investigator decision.

*Follow-Up Phase:* The Follow-Up Phase will begin immediately after the off-treatment assessments have been completed and will continue for up to 2 years or until study subject is deceased, or until the completion of the primary analysis, whichever is earlier, unless the subject withdraws consent or until the sponsor terminates the study. Information on AEs and concomitant medications will be collected for 90 days after the last dose of study drug or start day of another anticancer therapy, whichever is earlier. If the subject initiates new anticancer therapy within 30 days, then AEs and concomitant medications will be collected for 30 days following the last dose of E7766.

Subjects who discontinue study treatment before disease progression will continue to undergo disease assessment every 6 weeks in case of solid tumors and 12 weeks in case of lymphomas until documentation of disease progression or start of another anticancer therapy.

Subjects will be followed every 12 weeks (±1 week) for survival, performance status and subsequent anticancer treatments. The sponsor may decide to terminate survival follow-up anytime during the

Eisai Confidential Page 11 of 138

Extension Phase or when all subjects have discontinued study treatment. Survival follow-up will be conducted in person or via phone call.

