# 9.5.4.2 Reporting of Pregnancy and Exposure to Study Drug Through Breastfeeding

Any pregnancy in a female subject (or partner of a male subject) in which the estimated date of conception is either before the last visit or within 30 days of last study treatment, or any exposure to study drug through breastfeeding during study treatment or within 30 days of last study treatment, must be reported.

If an adverse outcome of a pregnancy is suspected to be related to study drug exposure, this should be reported regardless of the length of time that has passed since the exposure to study treatment.

A congenital anomaly, death during perinatal period, an induced abortion, or a spontaneous abortion are considered to be an SAE and should be reported in the same time frame and in the same format as all other SAEs (see Reporting of Serious Adverse Events [Section 9.5.4.1]).

Pregnancies or exposure to study drug through breastfeeding must be reported by fax or email as soon as possible but no later than 1 business day from the date the investigator becomes aware of the pregnancy. The contact information for the reporting of pregnancies and exposure to study drug through breastfeeding is provided in the Investigator Study File. The Pregnancy Report Form must be used for reporting. All pregnancies must be followed to outcome. The outcome of the pregnancy must be reported as soon as possible but no later than 1 business day from the date the investigator becomes aware of the outcome.

A subject who becomes pregnant must be withdrawn from the study. A subject who becomes pregnant may remain in the study if the investigator judges that the potential benefit to the subject outweighs any potential risk to the subject or the fetus and the subject gives informed consent for the further participation.

Eisai Confidential Page 96 of 138

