## 9.5.4.3 Reporting of Events Associated With Special Situations

9.5.4.3.1 REPORTING OF ADVERSE EVENTS ASSOCIATED WITH STUDY DRUG OVERDOSE, MISUSE, ABUSE, OR MEDICATION ERROR

Adverse events associated with study drug overdose, misuse, abuse, and medication error refer to AEs associated with uses of the study drug outside of that specified by the protocol. Overdose, misuse, abuse, and medication error are defined as follows:

Overdose Accidental or intentional use of the study drug in an amount higher

than the protocol-defined dose

Misuse Intentional and inappropriate use of study drug not in accordance with

the protocol

Abuse Sporadic or persistent intentional excessive use of study drug

accompanied by harmful physical or psychological effects

Medication error Any unintentional event that causes or leads to inappropriate study

drug use or subject harm while the study drug is in the control of site

personnel or the subject

All AEs associated with overdose, misuse, abuse, or medication error should be captured on the Adverse Event CRF and also reported using the procedures detailed in Reporting of Serious Adverse Events (Section 9.5.4.1) even if the AEs do not meet serious criteria. Abuse is always to be captured as an AE. If the AE associated with an overdose, misuse, abuse, or medication error does not meet serious criteria, it must still be reported using the SAE form and in an expedited manner but should be noted as nonserious on the SAE form and the Adverse Event CRF.

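### Protocol Sections 9.5.4.1 and 9.5.4.2 each give two unreconciled rules: two SAE reporting deadlines, and a pregnant subject who must be withdrawn yet may remain

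*Protocol*

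**What the plan says.** **SAE deadline.** Section 9.5.4.1 opens with two paragraphs that are the same except for the limit. Both cover every SAE whatever its relationship to treatment, and both ask for the SAE form as soon as possible. The first sets the limit at "no later than 1 business day from the date the investigator becomes aware of the event"; the second at "no later than 24 hours from when the investigator becomes aware of the event".

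Two other places depend on this deadline:

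- Section 9.5.4.2 treats congenital anomaly, perinatal death, and induced or spontaneous abortion as SAEs that "should be reported in the same time frame and in the same format as all other SAEs". It also sets a limit of its own: "The outcome of the pregnancy must be reported as soon as possible but no later than 1 business day".
- Section 9.5.4.3.1 requires AEs from overdose, misuse, abuse or medication error to be "reported using the procedures detailed in Reporting of Serious Adverse Events (Section 9.5.4.1) even if the AEs do not meet serious criteria".

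**Pregnancy.** Section 9.5.4.2 says "A subject who becomes pregnant must be withdrawn from the study". The next sentence begins "A subject who becomes pregnant may remain in the study if the investigator judges that the potential benefit" and goes on to require that benefit outweigh risk and that the subject consent.

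Elsewhere, pregnancy is a reason to stop study drug with no exception. The Extension Phase text of the synopsis ends its list of stopping reasons with "subject request, withdrawal of consent, termination of the study program, pregnancy, or investigator decision". Section 9.1.3.3, Figure 4 in Section 9.1.3, and Duration of Treatment in the synopsis also list pregnancy. The SAP is silent on both matters.

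**The concern.** Each pair gives a site two instructions for one situation.

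For SAEs, a site that works from the business-day paragraph can send a report that is on time under that paragraph and late under the next. A monitor has no single standard for calling a deviation.

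For pregnancy, a site cannot apply both sentences as written. It also cannot tell which of three courses is meant: the subject leaves the study, she stops study drug but stays in follow-up, or she may continue study drug.

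This is a first-in-human study run under several regulatory authorities, so safety reporting and the handling of pregnancy should be unambiguous. What is at stake is compliance with reporting rules, the handling of an individual subject, and the coding of disposition. Error rates, sample size and planned estimates are not involved.

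**Working it through.** There is no planned figure to reproduce. The check is a comparison of texts plus calendar arithmetic for the SAE limits.

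**1. Can the SAE paragraphs be separated by scope?** No. Both apply to all SAEs regardless of causality, by the same form and route. Neither names a region, country or site.

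**2. How far apart are the limits?** The protocol does not define a business day, so the following are assumptions: Monday-to-Friday business days; awareness between 09:00 and 17:00; and the limit ending on the next business day either at 17:00 or at midnight. Allowed time is the end of the next business day minus the time of awareness. The other paragraph always allows 24 h.

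| Day of awareness | Ends 17:00 (aware 17:00 to 09:00) | Ends midnight (aware 17:00 to 09:00) |
|---|---|---|
| Sunday to Thursday | 24 to 24 + 8 = 32 h | 24 + 7 = 31 to 24 + 15 = 39 h |
| Saturday | 48 to 48 + 8 = 56 h | 48 + 7 = 55 to 48 + 15 = 63 h |
| Friday | 72 to 72 + 8 = 80 h | 72 + 7 = 79 to 72 + 15 = 87 h |

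- Smallest excess over 24 h: 24 − 24 = 0 h.
- Largest excess: 87 − 24 = 63 h.
- A Monday holiday adds 24 h for awareness on Friday, Saturday or Sunday.

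Awareness outside 09:00 to 17:00 widens the range both ways. From the start of Friday to Monday midnight is 4 × 24 = 96 h, an excess of 72 h. From Monday 20:00 to Tuesday 17:00 is 21 h, so the business-day limit is then the shorter one by 3 h. Such awareness is realistic, because escalation subjects stay in the clinic for at least 30 hours after the first dose.

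**3. What depends on the unresolved limit?** Adverse pregnancy outcomes and special-situation AEs, through the cross-references to Section 9.5.4.1. Section 9.5.1.5.2 also routes pregnancy and other special situations through the SAE procedures.

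**4. Can the pregnancy sentences both hold?** Take each meaning of *remain* in turn.

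- *Remain includes treatment.* The second sentence contradicts the first. It also conflicts with the four places that make pregnancy an unconditional reason to stop study drug.
- *Remain means follow-up only.* The stop-drug lists are then satisfied, but the first sentence still requires withdrawal from the study itself.

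So the two sentences conflict under either meaning unless the second is an exception to the first, and it is not worded as one. The protocol has the vocabulary to be clear: Section 9.3.3 separates stopping treatment from leaving the study, and Duration of Treatment in the synopsis speaks of staying on treatment. Section 9.5.5 lists pregnancy among the primary reasons for discontinuing from the study, which shows that it can be a reason but does not say when it must be.

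**The case against.** **On the SAE pair**, both limits are upper bounds on the same act, and both paragraphs say as soon as possible. They can be met together: for awareness up to close of business, a report within 24 hours meets both. A late report requires a site to overlook the second paragraph, and urgent safety issues have a separate contact route. This makes the pair a lesser fault than the pregnancy one. It does not remove the ambiguity, because a site may reasonably take one paragraph as the rule meant for it.

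**On size**, the hours rest on assumed clock times that the protocol does not give. That is correct. The firm finding is that the limits diverge by about two to three days over a weekend; the exact hours are illustration.

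**On pregnancy outcomes**, the separate 1-business-day limit may govern a parallel report on the Pregnancy Report Form, and so need not conflict with the SAE time frame. That is a fair reading, but the text should say so.

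**On the pregnancy pair**, the second sentence is conditional and can be read as an exception, and the clash with the stop-drug lists arises only if remaining includes treatment. Both points stand. Even so, the first sentence is unqualified, nothing links the two, and an exception reading still leaves the meaning of remaining open. The reference to benefit to the subject makes a treatment reading plausible.

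**Conclusion.** The concern holds. The current protocol text gives two mandatory, unlabelled deadlines for the same SAE report, and two incompatible statements about a pregnant subject. Neither pair is resolved elsewhere.

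Under the stated daytime assumptions, the business-day limit exceeds the 24-hour limit by 0 to 63 h; after-hours awareness can extend or reverse the gap. The pregnancy contradiction is between two consecutive sentences. If remaining includes treatment, it extends to four stop-drug lists.

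The consequence is for safety reporting and subject handling, not for any analysis. The correction should be made. Its practical reach is limited to subjects still on treatment or in follow-up, because the SAP (Sections 3.2.2 and 7) records that escalation ended early and expansion will not enrol.

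**What to change.** - **Section 9.5.4.1:** keep one SAE deadline, or label each by the region to which it applies. If a business day is retained, define it.
- **Dependent text:** align Sections 9.5.4.2 and 9.5.4.3.1, and check Section 9.5.1.5.2. Say whether the pregnancy-outcome limit is a separate report or the same one.
- **Section 9.5.4.2, pregnancy:** reconcile the two sentences with each other and with the synopsis (Extension Phase and Duration of Treatment), Figure 4 and Section 9.1.3.3. State whether remaining means treatment or follow-up only, using the distinction in Section 9.3.3. Check the discontinuation reasons in Section 9.5.5 for consistency.

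Which deadline and which pregnancy rule apply is for the sponsor to decide; this review takes no position. The cost is wording only, with no new visit, sample or analysis.
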